Florbetapir scans were performed at baseline and after the last MAD, separated by approximately 7 months, to assess the PD effects of LY3002813. The change in grey matter standardized uptake value ratio (SUVr) with cerebellum as a reference region was compared across dose cohorts. There was a highly significant reduction in cerebral amyloid by PET at the highest dose (p<.0002). The analysis showed consistent reduction in cortical amyloid among patients receiving 3 to 5 doses of 10 mg/kg LY3002813. The mean reduction of 17% in SUVr corresponds to a mean 50% reduction in brain amyloid. Meaningful target engagement (amyloid reduction) was likely not achieved at doses smaller than or equal to 3 mg/kg IV every 4 weeks (Q4W) because of the rapid elimination of LY3002813 and the lack of sustained exposure.

More information about the known and expected benefits, risks, and reasonably anticipated AEs may be found in the Investigator's Brochure (IB). Information on AEs expected to be related to the investigational product may be found in Section 7 (Development Core Safety Information) of the IB.

5.2. Rationale and Justification for the Study

This is the second study with LY3002813 in patients with MCI due to AD or mild to moderate AD. Data from Study AACC indicated a dramatic reduction in cerebral amyloid (as assessed by florbetapir PET imaging) in the 6 patients who received 3 to 5 doses of 10 mg/kg of LY3002813 IV over 6 months, without cerebral vasogenic edema or microhemorrhage complications in this dose group. These positive results were accompanied by a high incidence of ADAs at all doses, as well as infusion reactions noted at doses ≤ 3 mg/kg. Dosing was stopped in the multiple-dose phase of Phase 1 Study I5T-MC-AACC (Study AACC) due to high prevalence of ADAs and unexpected rapid clearance of the study drug.

As a result of the significant target engagement (amyloid reduction by florbetapir PET) that was identified after 3 to 5 doses of LY3002813 10 mg/kg IV over 6 months, the current study is proposed to determine whether different dosing regimens (single-dose, short-term “induction” dosing with higher, more frequent dosing; and chronic dosing for maximal PD effect) can mitigate immunogenicity and immune safety issues, and produce sustained amyloid reduction. The aims of the study are to evaluate the effect of different dosing regimens on ADAs and amyloid plaque removal, and assess the relationship between PK, PD (amyloid removal), immunogenicity, and clinical safety. As a high prevalence of ADAs was observed in Study AACC, a risk management plan for immune safety will be incorporated into the clinical trial including at least 6 hours monitoring after completion of each infusion, a protocol for management of infusion reactions, and standardized data collection for infusion reaction AEs.

A favorable risk/benefit profile and dosing selection will support further development of LY3002813, including: (1) removal of amyloid consistent with Study AACC; (2) persistence of amyloid removal after completion of dosing; (3) acceptable clinical impact of ADAs; (4) manageable risk of clinically significant infusion reactions; and (5) low incidence of amyloid-related imaging abnormalities-edema (ARIA-E) and ARIA-H.

6. Objectives

6.1. Primary Objective

The primary objective is to assess the effect of LY3002813 on brain plaque load using florbetapir imaging.

6.2. Secondary Objectives

The secondary objectives are to:

- further evaluate the safety and PK of single and multiple doses of LY3002813 in Japanese and non-Japanese patients with MCI due to AD or mild to moderate AD
- evaluate the immunogenicity of single and multiple doses of LY3002813

6.3. Exploratory Objective

The exploratory objectives are to:

- assess the relationship among dosing regimens, PK, PD from florbetapir scan, immunogenicity, and immune safety
- evaluate changes in plasma, serum, and cerebrospinal fluid (CSF) biomarkers following single and multiple doses of LY3002813
- evaluate the effects of single and multiple doses of LY3002813 on cognitive function
- evaluate changes in MRI measures and 18F-AV-1451 tau PET scan
- evaluate genetic interactions with study treatment response or any AEs

7. Investigational Plan

7.1. Summary of Study Design

[figure not shown]
This is a Phase 1b, patient- and investigator-blind, randomized within cohort, placebo-controlled, parallel-group, single- and multiple-dose study in patients with MCI due to AD or mild to moderate AD to assess the safety, tolerability, PK, and PD of single and multiple IV doses of LY3002813.

This study (Study AACD) will enroll patients with MCI due to AD, mild AD, or moderate AD with amyloid deposition confirmed by florbetapir PET imaging using National Institute on Aging-Alzheimer's Association (NIAAA) work group consensus guidelines (Albert et al. 2011; McKhann et al. 2011). This study will be conducted at sites in multiple countries, including the United States and Japan. Up to 150 patients may be enrolled so that approximately 72 patients (7 dosing cohorts of 8 to 12 patients) complete the study.

[figure not shown]
The study will be conducted in at least 7 cohorts ([Figure AACD.7.1](#)):

- Cohort 1: 10 mg/kg IV single dose
- Cohort 2: 20 mg/kg IV single dose
- Cohort 3: 40 mg/kg IV single dose
- Cohort 4: 10 mg/kg IV every 2 weeks (Q2W) for 24 weeks
- Cohort 5: 20 mg/kg IV Q2W for 24 weeks
- Cohort 6: 10 mg/kg IV Q4W for up to 72 weeks
- Cohort 7: 20 mg/kg IV Q4W for up to 72 weeks

[figure not shown]
Part A: Single dose; 72-week follow-up (Cohorts 1 & 2), 24-week follow-up (Cohort 3)

Part B: 24-weeks, Q2W multiple dose treatment; 48-week follow-up

Part C: Chronic dose, 72-week, Q4W multiple dose treatment; 12-week follow-up

Abbreviations: f/u = follow up; IV = intravenous; MRI = magnetic resonance imaging; PET = positron emission tomography; Q2W = every 2 weeks; Q4W = every 4 weeks; x = times.

Assessments: A = amyloid PET; I = immunogenicity; M = MRI; T = tau PET; C = cognition; F = cerebrospinal fluid.

D = dosing; S = 4 week safety review of Cohort 2.

Follow-up assessments (immunogenicity, I; MRI, M) 12 weeks after last dose for Cohorts 6 and 7.

Note: vertical lines indicate 4-week intervals. Additional immunogenicity assessments will be performed every 12 weeks up to 48 weeks after the last dose of LY3002813 if the antibody titer has not returned to baseline.

Figure AACD.7.1. Study design.

Cohort 2 will only be initiated after review of safety data from Cohort 1. Thereafter, Cohort 3 will be initiated after review of safety data from Cohort 2. Cohorts 4 and 5 will be initiated after review of safety and PK data from their respective single-dose cohorts. An additional requirement for Cohort 5 is confirmation that at least 2 patients have received at least 3 doses each of LY3002813 safely in Cohort 4. Cohort 6 and Cohort 7 may proceed in parallel with Cohorts 4 and 5, respectively. In addition, Cohort 7 will only be initiated after confirmation that at least 2 patients have received at least 2 doses each of LY3002813 safely in Cohort 6.

Safety/PK reviews will occur after a minimum of 4 patients receiving LY3002813 and 1 patient receiving placebo have been dosed. For Cohorts 1 to 3, no more than 1 patient will be dosed on any one particular day. For Cohorts 4 to 7, patients dosed on the same day at any one site should not be dosed simultaneously but should be separated by at least 1 hour. Each cohort will contain approximately 6 (single dose) or 9 (multiple dose) patients treated with LY3002813 and 2 to 3 patients treated with placebo so that the study can detect target engagement and ADA frequency relative to those observed in Study AACC.

The primary target engagement outcome is the reduction of cerebral amyloid as measured by quantitative amyloid PET imaging (florbetapir SUV_r) assessed at baseline and at 12 weeks, 24 weeks, 36 weeks, 48 weeks, and 72 weeks after starting treatment. The early postbaseline scans are aimed to assess the time course of amyloid reduction; the later scans are aimed to assess sustainability of amyloid reduction after completion of dosing in Parts A and B, and maximal amyloid removal in Part C.

Safety and PK of LY3002813 will be assessed throughout the study for each cohort. In addition, blood samples for the assessment of immunogenicity will be taken at regular intervals throughout the dosing and follow-up periods. For Cohorts 1 through 3, a CSF sample will be taken by single lumbar puncture (LP) at baseline, another approximately 3 days after dosing to measure the CSF concentration of LY3002813 and CSF biomarkers. For Cohorts 4 through 7, a CSF sample will be taken by single LP at baseline and after 24 weeks dosing, or the last dose if treatment is stopped earlier.

As noted previously, a high prevalence of ADAs was observed in Study AACC; therefore, a risk management plan for immune safety is incorporated into the clinical trial. Other safety monitoring in Study AACD will include serial MRIs beginning at baseline and following dosing according to the study schedule for assessment of amyloid-related imaging abnormalities, AEs, ECGs, vital signs (blood pressure, pulse rate, and temperature), physical examinations, neurological examinations, and safety laboratory tests of blood (including immunogenicity).

Exploratory assessments include CSF, serum, and plasma biomarkers; cognitive function; MRI measures; 18F-AV-1451 tau PET scan (optional for Japan sites); and genetic interactions.

7.1.1. Screening for all Cohorts

At Visit 1, patients will undergo the screening tests outlined in [Attachment 1](#). Upon fulfilling the screening criteria at Visit 1, the patient will undergo a screening MRI (Visit 2) and then a screening florbetapir PET scan (Visit 3), sequentially, provided that the MRI criteria are met before the PET scan occurs. If the patient's eligibility is confirmed by a positive florbetapir PET

scan, then this scan serves as their baseline PET scan. Patients may undergo some or all of the predose testing, including cognitive testing and LP as an outpatient or inpatient (Visit 4). Cognitive testing requires a minimum of 4 hours rest between the Alzheimer's Disease Assessment Scale – Cognitive Subscale (ADAS-cog) and Neuropsychological Test Battery (NTB) to avoid test fatigue; ideally, cognitive testing should occur before LP if on the same day, and LP should occur no closer than 24 hours before dosing. However, LP could be performed as a separate visit, and cognitive testing can be performed after a minimum of 24 hours has passed after performing the LP, and patient must be free from any post-LP headache. Patients should be admitted on Day 1, but may be admitted to the site on Day -1 (the day before the first dosing day).

7.1.2. Dosing for all Cohorts

For each dosing day, patients will remain resident at the site for a minimum of 6 hours from the end of infusion, during which time patients will be monitored for safety and, in particular, for infusion reactions. If deemed necessary for safety or feasibility reasons, patients may remain at the site for a longer duration (including an overnight stay), at the discretion of the investigator.

7.1.3. Part A: Single Dose Cohorts (Cohorts 1 through 3)

Safety, PK, and PD will be assessed in Cohorts 1 through 3 after single doses of LY3002813 or placebo. The planned doses are 10, 20, and 40 mg/kg IV for Cohorts 1, 2, and 3, respectively; with 8 patients (6 LY3002813; 2 placebo) planned to be enrolled in each cohort. Dose escalation will only occur after the safety from the preceding cohort has been established in at least 4 patients receiving LY3002813 and 1 receiving placebo. Safety data will be collected at least 1 week after dosing for dose escalation to Cohort 2 and at least 4 weeks after dosing for dose escalation to Cohort 3. Enrollment in Cohorts 2 and 3 will only commence once enrollment into the preceding cohort has completed. Safety, PK, and PD will be assessed at regular intervals for approximately 72 weeks (in Cohorts 1 and 2) or 24 weeks (in Cohort 3) after starting the dosing with study drug ([Attachment 1](#)).

7.1.4. Part B: 24-Week Q2W Multiple Dose Cohorts (Cohorts 4 through 5)

Safety, PK, and PD will be assessed in Cohorts 4 and 5, during and after multiple doses of LY3002813 or placebo have been administered Q2W for 24 weeks. The planned doses are 10 and 20 mg/kg IV with 12 patients (9 LY3002813; 3 placebo) planned to be enrolled in each cohort. Cohort 4 (10 mg/kg IV Q2W for 24 weeks) will be initiated after review of the safety (at least 1 week after dosing) and PK data (complete Day 29 visit) from at least 4 patients receiving LY3002813 and 1 receiving placebo in Cohort 1. Cohort 5 (20 mg/kg IV Q2W for 24 weeks) will only be initiated after review of the safety and PK data (at least 4 weeks after dosing) from Cohort 2 in at least 4 patients receiving LY3002813 and 1 receiving placebo, and after confirmation that at least 2 patients have been dosed safely with LY3002813 at least 3 times each in Cohort 4. Safety and PD will be assessed at regular intervals for approximately 48 weeks after completion of 24 weeks of dosing with LY3002813 ([Attachment 1](#)).

7.1.5. Part C: Chronic, 72-Week Q4W Multiple Dose Cohorts (Cohorts 6 and 7)

Safety, PK, and PD will be assessed in Cohorts 6 and 7 during and after multiple doses of LY3002813 or placebo have been administered Q4W for up to 72 weeks, or when the LY3002813-induced reduction in amyloid measured by florbetapir reaches the maximum reduction (defined as SUVr <1.1 for 2 consecutive scans) (Joshi et al. 2015). The planned doses are 10 and 20 mg/kg IV with 12 patients (9 LY3002813; 3 placebo) planned to be enrolled in each cohort. Cohort 6 (10 mg/kg IV Q4W) and Cohort 7 (20 mg/kg IV Q4W) may proceed, in parallel with Cohorts 4 and 5, respectively. In addition, Cohort 7 will only be initiated after confirmation that at least 2 patients have received at least 2 doses each of LY3002813 safely in Cohort 6. The maximum dose of 20 mg/kg will not be exceeded. If a patient is deemed to be amyloid negative by florbetapir PET before completion of 18 months' dosing (SUVr <1.1 for 2 consecutive scans), the patient will receive placebo infusion for all subsequent visits and continue the Part C visit schedule, including assessment of sustained amyloid reduction at the scheduled PET scan assessments. Safety, PK, and PD will be assessed for all patients at regular intervals for approximately 12 weeks after completion of 72 weeks of dosing with LY3002813 ([Attachment 1](#)).

7.1.6. CSF Sampling for all Cohorts

CSF samples will be obtained by single LP. In Cohorts 1 through 3, the first CSF sample will be collected at baseline and a second collected approximately 3 days after dosing. In Cohorts 4 through 7, a CSF sample will be collected at baseline and a second collected after 24 weeks of dosing, or the last dose if treatment is stopped earlier. Baseline and post-treatment CSF samples will be analyzed for biomarkers. LY3002813 concentrations will only be measured in the post-treatment samples ([Attachment 1](#)).

7.1.7. Study Design for Japanese Patients

Sites in Japan will participate in this study to recruit Japanese patients.

At least 2 Japanese patients should be enrolled in each dose cohort for Cohorts 1, 2, 4, and 6. Assuming that the cohorts will be dosed based on safety reviews, it is intended that at least 3 Japanese patients will be enrolled in each dose cohort for Cohorts 3, 5, and 7; however, recruitment to a cohort will not be contingent upon fulfilling these requirements. At least 17 Japanese patients should be enrolled in the study when all cohorts are dosed. Japanese patient enrollment into cohorts should ensure sufficient exposures at applicable doses to support future studies (for example, at least 6 Japanese patients overall exposed to LY3002813, and at least 2 Japanese patients per cohort exposed to LY3002813 at the highest doses to be used in future studies). For the purpose of safety evaluation in Japanese patients during the study, Japanese patients at sites in Japan and up to third-generation Japanese patients at sites outside of Japan will be included. The definition of up-to-third-generation Japanese is defined in Section 8.1.

Evaluation of safety data from patients before dose escalation in Japan must include at least 1 Japanese patient on LY3002813. Therefore, if no Japanese patients are assigned to

LY3002813 in the cohort of patients evaluated before dose escalation, then dose escalation outside Japan will proceed, and additional Japanese patients will be recruited so that at least 1 Japanese patient will be on LY3002813 to allow dose escalation in Japan. To avoid unblinding, there must be at least 2 Japanese patients in a cohort. Once the Japanese patients have adequate 1-week or 4-week safety evaluations (as applicable), then patients in Japan may join in the ongoing dose-escalation cohort.

CSF collection is not required for Japanese patients when the required total number of patients has already been reached for the cohort.

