9.2.1. Method of Assignment to Treatment

A patient number will be assigned to each patient after the ICF is signed and dated. This identification number must appear on all patient-related documents. Assignment to treatment groups will be determined by a computer-generated random sequence within each dose cohort using an interactive web response system (IWRS).

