### Figure AACD.3.1. Study Design.

## 4. A Priori Statistical Methods

### 4.1. Determination of Sample Size

Up to approximately 150 patients may be enrolled to ensure that approximately 72 patients complete the study. Cohorts 1, 2, and 3 are each planned to have a minimum of 8 patients (6 LY3002813; 2 placebo) complete the study. Cohorts 4 and 5 are each planned to have a minimum of 12 patients (9 LY3002813; 3 placebo) complete the study. Also, Cohorts 6 and 7 are each planned to have a minimum of 12 patients (9 LY3002813; 3 placebo) complete the study.

The sample size is customary for studies evaluating safety, PK, and/or PD parameters; at the conclusion of the trial, confidence intervals (CIs) for PK, PD, and cognition endpoints may be computed in order to evaluate the precision of the estimates where appropriate. Based on prior Lilly clinical trials, 6 patients randomized to each LY3002813 dose and placebo provide over 90% power to detect at least a **CCI** mean SUVr reduction of a dose compared to that of placebo without multiple comparison adjustment. Based on Fixed and Adaptive Clinical Trial Simulator (FACTS) simulations, there is over 90% success rate that at least 1 LY3002813 dose separates from placebo with a success criterion of  $\Pr(\text{mean SUV}_r \text{ reduction of LY3002813 dose} < \text{mean SUV}_r \text{ reduction of placebo}) > \text{CCI}$ . If more patients are needed to determine safety, target engagement, PK, dosing, and/or race differences, then up to a total of 10 additional patients may be added.

In order to maintain a constant accrual rate, the randomization ratio will be 6:2 in Cohorts 1, 2, and 3; randomization will progress with a 9:3 ratio in Cohorts 4 to 7. It is intended that at least 2 Japanese patients will be enrolled in each dose cohort for Cohorts 2, 4, and 6. Assuming that the cohorts will be dosed based on safety reviews, it is intended that at least 3 Japanese patients will be enrolled in each dose cohort for Cohorts 3, 5, and 7. If the number of recruited Japanese patients per cohort is fewer than 3, then the randomization will continue. Japanese patients will continue to enroll with a 2:1 randomization ratio with the cohort. Details on the randomization plan will be described in the interactive web response system (IWRS).

This ratio is based on the enrolment rate of Study AACC.

Patients who are randomized but who do not complete the 12-week safety and PET assessment may be replaced.

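### When the Japan escalation rule fires on evaluated Japanese patients it reveals them as placebo, and no stated stratum or block secures the example per-cohort Japanese exposure

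*Protocol*

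**What the plan says.** Protocol 7.1.7 sets a condition for Japan: "Evaluation of safety data from patients before dose escalation in Japan must include at least 1 Japanese patient on LY3002813". If it is not met, "dose escalation outside Japan will proceed, and additional Japanese patients will be recruited so that at least 1 Japanese patient will be on LY3002813". The safeguard offered for the blind is: "To avoid unblinding, there must be at least 2 Japanese patients in a cohort".

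The planned numbers are "At least 2 Japanese patients should be enrolled in each dose cohort for Cohorts 1, 2, 4, and 6", and an intention that "at least 3 Japanese patients will be enrolled in each dose cohort for Cohorts 3, 5, and 7". The same section says recruitment to a cohort does not depend on reaching them. It also says Japanese enrollment should ensure sufficient exposure, giving as examples at least 6 Japanese patients on drug overall and "at least 2 Japanese patients per cohort exposed to LY3002813 at the highest doses to be used in future studies".

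On allocation, Protocol 9.2.1 says only that it is "determined by a computer-generated random sequence within each dose cohort", run through the IWRS. SAP 4.1 gives 6:2 for Cohorts 1 to 3 and 9:3 for Cohorts 4 to 7, and adds: "Japanese patients will continue to enroll with a 2:1 randomization ratio with the cohort". It leaves the remaining detail to the IWRS. Neither document names a Japanese stratum or a block size.

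Protocol 9.6 declares the study patient- and investigator-blind, and Attachment 4 keeps the site investigator blinded until database lock. Protocol 9.4 and 9.4.1 make the investigator a party to each escalation decision.

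**The concern.** The rule turns treatment assignment into something visible. Sites hold the protocol, and they see whether Japan opens with the other sites or waits. Once a wait is known to come from this rule, its meaning can be read from 7.1.7: no evaluated Japanese patient is on LY3002813.

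The 2-patient minimum helps in the other case. When Japan opens and only one Japanese patient has been evaluated, that patient is shown to be on drug; with two or more, nobody can tell which. When the rule fires, a second patient only raises the number revealed as placebo. If extra patients were then evaluated one at a time, lifting the hold would reveal the newest as being on LY3002813.

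The main exposure is in investigator-judged data such as adverse event relatedness and CDR ratings, rather than in quantitative PET. Separately, the per-cohort Japanese exposure that 7.1.7 wants for later studies rests on an allocation scheme whose relevant features are not stated.

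**Working it through.** **The plan's own figure.** Four cohorts of 2 plus three of 3: 4×2 + 3×3 = 17, matching the at least 17 in 7.1.7. SAP 4.1 omits Cohort 1 from the 2-patient minimum, giving 3×2 + 3×3 = 15. The plan states no probability for the Japan rule.

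**Inputs.** 6:2 and 9:3 (SAP 4.1); Japanese numbers at the 7.1.7 minimums; minimum review set of 4 on LY3002813 and 1 on placebo (Protocol 7.1, 9.4). Assumption: Japanese patients are a random subset of a cohort filled to its exact ratio.

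**Step 1. Both of 2 Japanese patients on placebo, full cohort.**
- 6:2: C(2,2)/C(8,2) = 1/28 = 3.6%.
- 9:3: C(3,2)/C(12,2) = 3/66 = 4.5%.

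**Step 2. At least one such event.**
- Cohorts 1 and 2 as gates: 1 − (27/28)² = 7.0%.
- Cohorts 4 and 6 as well: 1 − (27/28)²(21/22)² = 15.3%.
- Simple 3:1 randomisation over four gates: 1 − (15/16)⁴ = 22.8%. Simple 2:1: 1 − (8/9)⁴ = 37.6%.

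**Step 3. Minimum review set (4 + 1).** With 2 Japanese patients and a single placebo, both cannot be on placebo: 0%. With 1 Japanese patient: 1/5 = 20%, and that person is identified. With none, the condition is unmet but nothing is revealed.

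**Step 4. At least 2 of exactly 3 Japanese patients on LY3002813.**
- Cohort 3: [C(6,3) + C(6,2)·C(2,1)]/C(8,3) = (20 + 30)/56 = 89.3%.
- Cohorts 5 and 7, each: [C(9,3) + C(9,2)·C(3,1)]/C(12,3) = (84 + 108)/220 = 87.3%.
- All three: 0.893 × 0.873² = 68.0%. Simple 3:1 gives 60.1%; simple 2:1 gives 40.6%.

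**Step 5. At least 6 of 17 on LY3002813.** 99.999% under fixed cohort ratios; 99.8% even under simple 2:1.

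**Step 6. Effect of a Japanese stratum, by block.**

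| Block in Japanese stratum | First 2 both placebo | At least 2 of first 3 on drug |
|---|---|---|
| 4 (3:1) | 0 | 100% |
| 3 (2:1) | 0 | 100% |
| 8 (6:2) | 3.6% | 89.3% |
| 6 (4:2) | 6.7% | 80.0% |

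The gain comes from having one placebo per block, not from stratifying as such. With one Japanese patient evaluated, a block of 4 still leaves a 1/4 = 25% chance that the rule fires.

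**The case against.** Much of the opposing case stands.

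- **Scope.** A reader might infer that a hold exposes every Japanese patient so far. The rule concerns only the patients evaluated before escalation. A hold can also arise with no Japanese patient in that set, with fewer than 2 in the cohort, or with their 1- or 4-week evaluations incomplete. A hold is informative only if its cause is known.
- **Sufficiency.** 7.1.7 says there must be at least 2 Japanese patients; it does not say that 2 are enough. That is correct, but the section offers no other protection for the blind.
- **Size.** A reader might take 15.3% as the chance that the rule fires. It assumes full cohorts and four gates. The 1- and 4-week evaluations match the Cohort 1 and 2 reviews, while the conditions tied to Cohorts 4 and 6 count doses given safely. On that reading the figure is 7.0%, and smaller review sets can bring it to zero.
- **Stratification.** A reader might conclude that allocation is unstratified. The documents show only that no stratum is stated. The SAP's 2:1, if run as a block of 3, would give exactly 2 of 3 on drug.
- **Exposure.** The target is an example, and the future doses are unnamed. SAP 4.1 continues randomisation below 3 Japanese patients, and Protocol 11.1 allows up to 10 additional patients, so a shortfall could be repaired.

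What remains is that the rule, once it fires on evaluated Japanese patients, discloses their assignment, and that neither document states a feature that prevents this or delivers the per-cohort figure.

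**Conclusion.** The concern holds in a limited form. If at least one Japanese patient is evaluated, none is on LY3002813, and the cause of the Japan hold is known, the evaluated Japanese patients are revealed as placebo. The 2-patient minimum does not stop this.

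Without a Japanese stratum the chance is 3.6% or 4.5% per full cohort with 2 Japanese patients: 7.0% over Cohorts 1 and 2, at most 15.3% over four gates under fixed cohort ratios, and zero in a 4 + 1 review set. Simple randomisation would be worse. The example of 2 Japanese patients on drug is met with probability 89% in Cohort 3 and 87% in each of Cohorts 5 and 7. The joint 68% requires exactly 3 Japanese patients per cohort, no additions, and all three cohorts counting as highest doses. At least 6 overall is not in doubt.

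It would be tempting to say that stratifying cures both problems. It does not: it makes firing rarer, leaves what firing reveals unchanged, and secures exposure only with one placebo per block and the planned Japanese numbers enrolled. The change is worth making because it is cheap; the defect does not threaten the primary comparison.

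**What to change.** 1. In Protocol 9.2.1 and SAP 4.1, stratify randomisation within cohort by Japanese/non-Japanese, using the 7.1.7 definition, at 3:1 from the first patient. Put the block (one placebo per block in the Japanese stratum, for example 3 + 1) only in the restricted IWRS specification. A block size known to sites would let them deduce the rest of a block once one placebo patient is known. The first 2 Japanese patients then include at least 1 on LY3002813, and the first 3 at least 2.
2. Reconcile this with the SAP's 2:1 continuation ratio, and the SAP's Japanese minimums with those in 7.1.7 (15 against 17).
3. Because the rule can still fire with 0 or 1 Japanese patients evaluated, have sponsor staff who are already unblinded under Attachment 4 apply the Japan condition, and tell sites only whether Japan is open, not why.
4. Reword 7.1.7 so that the 2-patient minimum is not presented as the protection of the blind. The escalation conditions themselves need not change.

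**Cost.** An IWRS list change and a few sentences. Cohort totals may differ by about one patient from 6:2 or 9:3. For example, with blocks of 4 in both strata and 2 Japanese patients among 8, the placebo count is 1 + X + Y, where X and Y are each 0 or 1 with probability 1/2. That gives 1, 2 or 3 placebo patients with probability 25%, 50% and 25%.
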